For the primary efficacy endpoint, a minimum of 172 subjects are needed in each treatment arm to detect non-inferiority of bexagliflozin to glimepiride with respect to the change in HbA1c from baseline at week 60 by a margin of 0.35%, assuming an estimated pooled standard deviation of 1.0%. This estimation is based on a one-sided t-test with 90% power at a 0.025 level of significance. To allow for an estimated 18.0% dropout rate, 210 patients will be randomized in each treatment arm, and the total sample size will be 420 subjects for this study.

Statistical analyses and summaries will be performed using SAS[®] software (SAS Institute, Cary, NC).

LIST OF ABBREVIATIONS AND DEFINITIONS OF TERMS

ADA	American Diabetes Association
AE	adverse event
ALB	albumin
ALT	alanine aminotransferase
ANCOVA	analysis of covariance
AST	aspartate aminotransferase
ATC	Anatomic Therapeutic Chemical classification
BMI	body mass index
BP	blood pressure
BUN	blood urea nitrogen
CEC	cardiovascular endpoint committee
CFR	Code of Federal Regulations
CI	confidence interval
CRF	case report form
CRO	contract research organization
DKA	diabetic ketoacidosis
CYP	cytochrome P450
DPP4	dipeptidyl peptidase-4
DSMB	data and safety monitoring board
ECG	electrocardiogram
eGFR	estimating glomerular filtration rate
FPG	fasting plasma glucose
GCP	Good Clinical Practice
GI	gastrointestinal
GLP-1	glucagon-like peptide-1
GMI	genital mycotic infection
h	hour
HbA1c	hemoglobin A1c
HBsAg	hepatitis B surface antigen
Hct	hematocrit
HCV	hepatitis C virus
HDL-C	high density lipoprotein cholesterol
HDPE	high-density polyethylene
Hgb	hemoglobin
HIV	human immunodeficiency virus
ICH	International Conference on Harmonisation

IEC	independent ethics committee
IND	Investigational New Drug application
IRAE	immediately reportable adverse event
IRB	institutional review board
ITT	intention-to-treat
IWRS	Interactive Web Response System
LDL-C	low density lipoprotein cholesterol
LOCF	last observation carried forward
MACE	major adverse cardiovascular event
MCH	mean corpuscular hemoglobin
MCHC	mean corpuscular hemoglobin concentration
MCV	mean corpuscular volume
MDRD	modification of diet in renal disease
MedDRA	medical dictionary for regulatory activities
MI	myocardial infarction
MMRM	mixed model repeated measures
MODY	maturity-onset diabetes of the young
N	number of subjects
NYHA	New York Heart Association
OHA	oral hypoglycemic agent
PO	per oral
PP	per protocol

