3.8. DETERMINATION OF SAMPLE SIZE

An approximate total of 420 subjects will be randomized and equally allocated to receive:

- bexagliflozin tablets, 20 mg and glimepiride, placebo capsules (referred to as bexagliflozin group in this document)
- bexagliflozin tablets, placebo and glimepiride capsules, 2 mg, 4 mg, or 6 mg (referred to as glimepiride group in this document).

The sample size calculation for this study is based on a two group t-test with a one-sided significance at the 0.025 level and the following assumptions:

- The non-inferiority limit (margin) for mean change from baseline to week 60 in HbA_{1c} comparing bexagliflozin group to glimepiride group will be 0.35%
- The standard deviation for the change from baseline to week 60 in HbA_{1c} for bexagliflozin group and glimepiride group will be 1.0%

Under the above assumptions, an estimated sample size of 172 subjects is needed in each treatment arm to determine non-inferiority of bexagliflozin to glimepiride with respect to change in HbA_{1c} at week 60 from baseline. This estimation is based on a one-sided t-test with 90% power at a 0.025 level of significance. A sample size of 210 per arm has been selected to account for approximate 18% drop-out rate and to allow adequate safety evaluation. The total sample size for this study will be 420 subjects.

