treatment arms (using the MCMC statement in PROC MI). Multiple chains option (CHAIN=MULTIPLE option in the MCMC statement of PROC MI) will be used. For the non-monotone imputation of the HbA_{1c} missing data, a multivariate normal model will be used including variables for the HbA_{1c} at baseline and all post-baseline visits within each treatment group. Five hundred imputed datasets will be generated.

2. After the non-monotone missing data have been imputed, the remaining monotone missing data will be imputed within each treatment arm and subgroup, defined by whether subject completed 60 week of study treatment, using regression approach. The predictors for the regression imputation model at any time point will be region, treatment background (metformin only or metformin and OHA), baseline eGRF (≥ 90 or < 90 ml/min/1.73 m²), and HbA_{1c} at all previous time points, including baseline. Imputations will be performed using a sequence of regression-based imputations (using PROC MI statement MONOTONE REG) at each post-baseline time point.
3. Imputed data in each of the multiple imputed datasets will be analyzed using a mixed model repeated measures (MMRM) approach. The MMRM model will include region, terms for treatment background (metformin only or metformin and OHA), baseline eGRF (≥ 90 or < 90 ml/min/1.73 m²), treatment, visit, treatment-by-visit interaction, and the baseline HbA_{1c} value, as a fixed effect covariate. The analysis will evaluate the mean change from baseline in HbA_{1c} over the 60-week double blind treatment period. An unstructured covariance will be used to model the within subject correlation. The Kenward Roger approximation will be used to estimate denominator degrees of freedom. If the model with the unstructured covariance structure does not converge, an autoregressive(1) covariance structure will be used. HbA_{1c} values obtained after the start of rescue medication will not be excluded from the analysis. The treatment and treatment by visit interaction terms allow for comparisons of the treatment groups at each visit, and over week 12 to week 60. Least squares (LS) mean treatment differences between the bexagliflozin group and the placebo group at week 60 will be estimated from the model. The LS mean results from all imputed datasets will be combined using the Rubin's combination rule (PROC MIANALYZE).

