If no sufficient week 60 values from treatment discontinued subjects are available for imputation, MMRM analysis as in step 3 will be performed using all available data.

Sample SAS code will be provided in Appendix.

In non-inferiority analysis, a CI is calculated to estimate the range of values in which the treatment difference is likely to lie. This CI is used to provide the basis for drawing the study's conclusions. In this specific test, if the 95% CI lies below the specified non-inferiority margin 0.35%, the results would lead to a conclusion of non-inferiority of

bexagliflozin treatment to glimepiride treatment. Lower HbA_{1c} value indicates improvement on subject diabetes condition. Larger decrease would indicate better treatment effect of bexagliflozin compared to glimepiride. Hence, superiority of bexagliflozin group over glimepiride group at week 60 in HbA_{1c} change from baseline will be declared if the upper bound of 95% CI is less than 0.

Descriptive statistics (n, mean, Q1, median, Q3, SD, minimum, and maximum) will be reported by treatment group and visit, along with the least squares means, differences between LS means, a 2-sided 95% confidence interval for each difference, p-values from the model effects. In addition, the LS means with standard errors of the change from baseline over time and difference between treatment groups with 95% will be presented graphically for the ITT population.

For supportive analyses, regardless of having sufficient week 24 values from treatment discontinued subjects are available for imputation or not, MMRM analysis will be performed using all available data. The primary efficacy endpoint will also be analyzed with all observed available data using MMRM method for the PP analysis set.

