8.2. SECONDARY EFFICACY ENDPOINT(S) AND ANALYSES

The secondary endpoints will only be tested when the non-inferiority of the primary efficacy assessment is established at one-sided significance level of 0.025. To control the overall type I error of 0.05, the secondary efficacy objectives will be tested at one-sided 0.025 significance level following the sequence below:

- Superiority test of the change in body weight in subjects with baseline body mass index (BMI) ≥ 25 kg/m² at week 60.
- Superiority test of the change in SBP in subjects with baseline SBP ≥ 140 mmHg from baseline at week 60.
- Superiority test of the difference in proportion of subjects with ≥ 1 severe or documented symptomatic hypoglycemia events over 96 weeks

Analysis for secondary endpoints will be based on ITT analysis set and repeated for PP analysis set. For body weight and SBP, all post-baseline values up to week 60 will be used for model analysis. All values will be summarized.

8.2.1. Change in body weight in subjects with baseline body mass index (BMI) ≥ 25 kg/m² at week 60

This will be tested if the non-inferiority of HbA_{1c} and the previous secondary efficacy endpoints are significant. Data after rescue medication will not be excluded. The comparison of change in body weight between randomized treatments at week 60 will be carried out using the similar MMRM model as section 8.1.1 using all available data. The model will include terms for region, treatment, baseline HbA_{1c} as continuous variable, treatment background (metformin-only or metformin-and-OHA), and baseline eGFR (≥ 90 or < 90 mL/min/1.73 m²) as fixed effects and the corresponding baseline weight value as covariate. Treatment comparison p-values and difference at week 60 will be estimated from the model, with the two-sided 95 % CIs of the treatment difference also presented. If the superiority of HbA_{1c} is not established, the nominal p-value will not be used for inferential purposes. Summary table will be presented and figures will be displayed for ITT population.

8.2.2. Change in SBP in subjects with baseline SBP ≥ 140 mmHg from baseline at week 60

This will be tested if the change from baseline body weight is significantly different between bexagliflozin and glimepiride groups based on ITT analysis set for subjects with a BMI ≥ 25 kg/m². Change from baseline in SBP at week 60 will be analyzed in a similar manner as change in body weight, Section 8.2.1, based on ITT analysis set for all

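### The only fallback if the unstructured MMRM fails is plain AR(1), which keeps the one-sided 2.5% level only if HbA1c spread is flat or falling over follow-up

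*SAP*

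**What the plan says.** SAP 8.1.1, step 3, fits an MMRM to the change in HbA1c with unstructured covariance and Kenward-Roger degrees of freedom. It then adds: "If the model with the unstructured covariance structure does not converge, an autoregressive(1) covariance structure will be used". Protocol 9.5.2 and the Synopsis carry the same fallback. Neither document names a structure with a separate variance per visit, an intermediate structure, or an empirical standard error.

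Step 3 produces the week-60 interval on which the trial is judged. Non-inferiority is concluded "if the 95% CI lies below the specified non-inferiority margin 0.35" (per cent HbA1c), and superiority if the upper bound is below 0. The same model is applied to each imputed dataset. It is also applied to all available data if too few treatment discontinuers have week-60 values to support the imputation.

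SAP 8.2.1 analyses body weight "using the similar MMRM model as section 8.1.1 using all available data", and 8.2.2 treats SBP in the same manner. Both belong to the formal testing sequence in SAP 8.2.

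**The concern.** Plain AR(1) estimates one variance and applies it to every visit. If the spread of HbA1c change grows during follow-up, that pooled variance is smaller than the week-60 variance. The standard error of the week-60 difference is then too small, and the upper confidence limit sits too low. The error favours the non-inferiority claim, and equally a superiority claim.

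Kenward-Roger does not remove the problem. It adjusts for small samples, taking the chosen covariance structure as correct. If spread is flat there is no problem, and if it falls the test becomes conservative. What is at stake is whether the 2.5% level holds in the event that the fallback is used.

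**Working it through.** **Inputs from the documents**
- Test level: "two group t-test with a one-sided significance at the 0.025 level" (SAP 3.8).
- Power: "This estimation is based on a one-sided t-test with 90% power at a 0.025 level of significance" (SAP 3.8).
- SD: "assuming an estimated pooled standard deviation of 1.0" per cent (Protocol Synopsis). It refers to the change at week 60, and no SD is given for weeks 12 to 48.
- Evaluable size: "an estimated sample size of 172 subjects is needed in each treatment arm" (SAP 3.8).
- Randomized size: "A sample size of 210 per arm has been selected to account for approximate 18% drop-out rate" (SAP 3.8).
- HbA1c visits up to week 60: weeks 12, 24, 36, 48 and 60 (SAP Table 1), equally spaced.

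**Reproducing the plan's own figure.** With a true difference of 0 (implied, not stated), n = 2 × (1.960 + 1.282)² × 1.0² / 0.35² = 171.6, so 172 per arm. Then 172 / (1 − 0.18) = 209.8, so 210. Both figures agree with the plan.

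**Assumption for the check.** The week-60 SD is 1.0 and the SD changes linearly from a week-12 value. Only the ratio of the SDs matters for the error rate.

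**Formulas**
- True SE at week 60, complete data, 210 per arm: √(2 × 1.0² / 210) = 0.0976.
- Approximate ratio of AR(1) SE to true SE: R = √(mean of the five visit variances) / SD at week 60.
- One-sided error at the margin: 1 − Φ(1.96 × R).

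**Worked case, SD rising from 0.8 to 1.0.** The SDs are 0.80, 0.85, 0.90, 0.95 and 1.00. The variances 0.6400, 0.7225, 0.8100, 0.9025 and 1.0000 have mean 0.815. R = √0.815 = 0.903, and 1 − Φ(1.770) = 3.8%.

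The AR(1) model was also fitted by maximum likelihood to the assumed covariances, under AR, compound-symmetry and mixed true correlations. Complete-data results, with the error range under 18% monotone dropout completely at random:

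| Week-12 SD | AR(1) SE | Ratio to true SE | One-sided error | 95% CI coverage | Error with 18% dropout |
|---|---|---|---|---|---|
| 1.2 | 0.1076 | 1.10 | 1.5% | 96.9% | 1.4–1.5% |
| 1.0 | 0.0976 | 1.00 | 2.5% | 95.0% | 2.3–2.5% |
| 0.9 | 0.0928 | 0.95 | 3.1% | 93.8% | 3.0–3.2% |
| 0.8 | 0.0882 | 0.90 | 3.8% | 92.3% | 3.8–3.9% |
| 0.7 | 0.0838 | 0.86 | 4.6% | 90.8% | 4.6–4.8% |

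For a week-12 SD of 0.7 the formula gives 4.7% and the full fit 4.6%. The true correlation pattern hardly matters; the unequal variances drive the result.

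**Effect of imputation.** Under Rubin's rules only the within-imputation variance is affected. If the between-imputation part is 10% of the total (assumed), the 0.8 case becomes √(0.9 × 0.815 + 0.1) = 0.913, and the error 1 − Φ(1.96 × 0.913) = 3.7%.

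**Effect of the fix.** A heterogeneous AR(1) fitted to the same scenarios gives SE ratios of 1.000 to 1.015 and one-sided errors of 2.3% to 2.5% throughout.

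**How likely the fallback is.** An unstructured matrix has k(k + 1)/2 parameters. For HbA1c, k = 5 gives 15 parameters with about 420 subjects. SBP is measured at weeks 2, 4, 6, 12, 24, 36, 48 and 60, so k = 8 gives 36 parameters, in an endpoint defined only for subjects with baseline SBP of at least 140 mmHg. These visits are unequally spaced, and AR(1) by visit order treats a 2-week gap like a 12-week gap. No SBP error rate was computed, because the documents give no SBP variances.

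**The case against.** **The trigger is remote for the primary test.** This stands. Fifteen covariance parameters with about 420 subjects, and complete datasets after imputation, should rarely fail to converge. With an assumed 1% chance of failure, the 3.8% case moves the overall level only to 0.99 × 2.5% + 0.01 × 3.8% = 2.51%.

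**Growing spread is not in the documents.** This also stands. A reader might infer from the larger errors in the table that the non-inferiority test runs at 4% to 5%. The documents do not support that: they give one SD at one time point, and flat or falling spread gives no inflation. Tightening rescue thresholds with post-rescue values retained could limit late spread. On the other side, the model adjusts for baseline HbA1c. If raw variance is stable and correlation with baseline fades, residual variance rises over time. That makes growth plausible but does not establish it.

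**Constant variance is inferred from the name.** Partly stands. SAP 8.1.1 refers to sample SAS code in an appendix that is not in the available text and could specify a heterogeneous form. The SAP wording does not.

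**Wider reach.** A reader might extend the point to the subgroup and per-protocol models. SAP 8.1.3 says that subgroup p-values carry no inference, and the per-protocol analysis is supportive, so no formal level is at stake in either. The SAP Table 3 window that could map stray HbA1c samples to week 6 is a separate visit-mapping matter. SBP is the reach that counts, and it depends on reading the similar model as including the fallback.

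**The plan already has a deterministic rule.** True, and that is to its credit. What remains is the choice of structure within that rule.

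**Conclusion.** The point holds as a conditional refinement. If plain AR(1) is used and spread rises to a week-60 SD of 1.0, the one-sided error is about 3.1% to 4.6% for week-12 SDs of 0.9 to 0.7. It is 2.5% with flat spread and about 1.5% if the SD falls from 1.2. These figures rest on three assumptions: the linear SD path, the usual constant-variance meaning of AR(1) in SAS, and the fallback being used in every dataset analysed. Imputation dilutes the effect slightly.

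For the primary HbA1c analysis the practical risk is small because the fallback is unlikely to be needed. The SBP test is more exposed, and it gates the hypoglycemia test, but the size of the effect there is unknown. Severity is low: a cheap improvement. No change to the sample size follows.

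**What to change.** In SAP 8.1.1, step 3, replace the AR(1) fallback with an ordered pair: heterogeneous Toeplitz, then heterogeneous AR(1). Keep Kenward-Roger. State that if any imputed dataset needs a fallback, the same structure is used in all of them, so that Rubin's rules combine like with like. Say in 8.2.1 and 8.2.2 whether this rule applies to body weight and SBP. Check that the SAS appendix agrees, and record the change in SAP section 13, since Protocol 9.5.2 names AR(1). Make the change before unblinding.

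The cost is a line or two of text and a few more covariance parameters. For five visits, heterogeneous Toeplitz needs 5 + 4 = 9 and heterogeneous AR(1) 5 + 1 = 6, against 2 for plain AR(1) and 15 for unstructured. For eight SBP visits the first two counts are 8 + 7 = 15 and 8 + 1 = 9. Both structures still index correlation by visit order, so they correct the variance assumption but not the unequal spacing of the SBP visits.

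Empirical standard errors are optional. They would need a different degrees-of-freedom rule and tend to be too small in small samples, which is a drawback in the SBP subset.

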8.1.2. Sensitivity Analyses

Randomized subjects who withdraw consent to participate in the study will not be replaced. The early withdrawal rate is estimated to be 18%. To the extent possible, attempts will be made to minimize the amount of missing data through measures planned in the study conduct.

To investigate the possible implications of missing values in efficacy assessments, the number, timing, pattern, and reason for the missing value will be summarized. The reason for withdrawal will be reviewed. If there are missing values for the primary analysis described in section 8.1.1, only available data will be analyzed and data obtained after rescue will not be excluded.

The dropout patterns will be assessed by a Kaplan-Meier plot of time to discontinuation by treatment group to assess whether they differ between treatment groups.

To evaluate the impact from missing data and rescue medication, the following sensitivity analyses will be conducted:

- 1) Tipping point analysis will be conducted. Data after rescue medication will be considered as missing. The following steps will be implemented:
 - a. Create monotone missing data as step a in the primary analysis in section 8.1.1 with 100 imputed datasets;
 - b. Regression approach under MAR will be used to generate complete datasets. The predictors for the regression imputation model at any time point will be region,

treatment background (metformin only or metformin and OHA), baseline eGFR (≥ 90 or < 90 mL/min/1.73 m²), treatment, and HbA_{1c} at all previous time points, including baseline. The first imputed values will be penalized or rewarded based on the treatment subject received:

- Subjects in the bexagliflozin group: missing value will be analyzed assuming the treatment effect is worsened by δ_1 (where $\delta_1 = 0.1$ to 0.5 , in step of 0.1) compared to the subjects who have no missing value in the reduction of HbA_{1c} value;
- Subjects in the glimepiride group: missing value will be analyzed assuming the treatment effect is better by δ_2 (where $\delta_2 = 0.1$ to 0.5 , in step of 0.1) compared to the subjects who have no missing value in the reduction of HbA_{1c} value;

The penalty or reward will not be applied to the values from later time points as these values are penalized or rewarded through regression on previous time points.

- c. Imputed datasets will be analyzed and results combined as step 3 in section 8.1.1.

For each combination of (δ_1 , δ_2), 100 imputed datasets will be obtained. These 25 combinations will be separately analyzed to explore under which condition where the null hypothesis can no longer having evidence to be rejected.

- 2) Additionally, the impact of the data after the start of rescue medication will be evaluated. HbA_{1c} values collected after the start of rescue medication will be considered missing, and the MMRM analyses will be performed. Same statistics provided for the primary analysis will be presented.

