9.5.2 Statistical Methods for Primary Analyses

For the primary endpoint, the treatment difference will be examined by using a mixed model repeated measures (MMRM) analysis of covariance model (ANCOVA). The model will include treatment, visit, treatment-by-visit interaction and randomization stratification factors as the fixed effects terms and the baseline HbA1c value as a fixed effect covariate. Least squares mean treatment differences between the bexagliflozin group and the comparator group at week 60 will be estimated from the model. An unstructured covariance will be used to model the within-subject correlation. If the model with the unstructured covariance structure does not converge, an autoregressive(1) covariance structure will be used.

HbA1c values obtained after the start of rescue medication will not be excluded in the analysis. These analyses will be conducted on both ITT (primary) and PP analysis sets, and conclusions can be considered more robust when both approaches support the non-inferiority of the treatment.

In non-inferiority analysis, a CI is calculated to estimate the range of values in which the treatment difference is likely to lie. This CI is used to provide the basis for drawing the study's conclusions. In this specific test, if the 95% CI lies below the specified non-inferiority margin 0.35%, the results would lead to a conclusion of non-inferiority of bexagliflozin treatment to glimepiride treatment. Superiority of bexagliflozin group over

glimepiride group at week 60 in HbA1c change from baseline will be declared if the upper bound of 95% CI is less than 0.

Sensitivity analyses will also be performed as the following, and these analyses will be conducted for ITT and PP analysis sets.

1. Missing data will be imputed via multiple imputations, following which the MMRM will be repeated on the complete datasets with results combined across complete datasets using standard MI techniques; HbA1c values collected after the start of rescue medication will not be excluded.
2. Missing data will be imputed via LOCF, following which the MMRM will be repeated; HbA1c values collected after the start of rescue medication will be considered missing.
3. HbA1c values collected after the start of rescue medication will be considered missing, and the MMRM analyses will be re-performed.

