8.1.1. Primary Efficacy Analysis

Let $\mu_{\text{bexagliflozin}}$ and $\mu_{\text{glimepiride}}$ represent the mean changes from baseline in HbA_{1c} at Week 60 for bexagliflozin and comparator groups, respectively. The following hypotheses will be tested:

$$H_0: \mu_{\text{bexagliflozin}} - \mu_{\text{glimepiride}} > \delta \text{ versus}$$

$$H_1: \mu_{\text{bexagliflozin}} - \mu_{\text{glimepiride}} \leq \delta$$

Non-inferiority margin δ is chosen to be 0.35% using clinical judgment, with reference to relevant regulatory guidance, and justified by published glimepiride efficacy study (Charpentier et al. 2001).

This hypothesis will be tested based on ITT analysis set. Missing data will be imputed via multiple imputations, following which the MMRM will be repeated on the complete datasets with results combined across complete datasets using standard multiple imputations techniques; HbA_{1c} values collected after the start of rescue medication will not be excluded. A pattern-mixture model will be used to explore the impact of the missing data. Imputation will be conducted within each treatment arm and subgroup (treatment completer vs. treatment terminated early) under the assumption that non-adherent subjects with missing data will follow the same trajectory of non-adherent subjects with values observed. All efforts will be made to retain subjects in the study. If treatment is discontinued, subjects are encouraged to remain in the study and complete all scheduled visits, including final follow-up visit. However, with all efforts, insufficient values may be available for reliable imputation. This analysis will be performed only if $\geq 3\%$ (approximately 6) of subjects in each treatment arm completed scheduled week 60 visit after treatment is stopped. This number is chosen to allow sufficient data to establish a regression model for imputation. For this analysis, the following three-step approach outlined below will be used:

1. Non-monotone (intermediate visits) missing data will be imputed first using the Monte Carlo Markov Chain (MCMC) method under the MAR assumption in all

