8.2.4. Sensitivity analysis

For all secondary analysis of body weight and SBP, missing data will be imputed via multiple imputations, following which the MMRM will be repeated on the complete datasets with results combined across complete datasets using standard multiple imputations techniques; Values collected after the start of rescue medication will be considered missing. Imputation steps include:

- a. Create monotone missing data as step a of section 8.1.1 with 100 imputed datasets;
- b. Regression approach under MAR will be used to generate complete datasets. The predictors for the regression imputation model at any time point will be region, treatment background (metformin only or metformin and OHA), baseline eGRF (≥ 90 or < 90 ml/min/1.73 m²), treatment, and values at all previous time points, including baseline. Values at each visit will be imputed sequentially. The first imputed values for subjects in bexagliflozin arm will be penalized by the mean improvement at week 60 on that endpoint (i.e. the mean change from baseline at week 60). Imputed values for subjects in glimepiride will not be penalized. Imputed values after the first missing value will be penalized through regression on first penalized value.
- c. Imputed datasets will be analyzed and results combined as in step c in section 8.1.1.

For the sensitivity analyses of proportion of subjects with hypoglycemia event, to account for subject discontinuation, incidence rate will be analyzed using negative binomial regression model. Data collected after the start of rescue medication will be considered as missing. The number of severe or documented symptomatic

hypoglycemia events will be used as outcome. Model will include region, treatment background (metformin only or metformin and OHA), baseline eGRF (≥ 90 or < 90 ml/min/1.73 m²), treatment, and baseline HbA_{1c} as fixed effect and the logarithm of the duration from first dose of double-blind treatment to date of week 96 visit as offset. If subject discontinued before week 96 visit, the date of discontinuation will be used. If subject used rescue medication, the last date before rescue medication will be used. The adjusted mean incidence over 96 weeks, 95% CI for each treatment arm, the risk ratio, 95% CI, and p-value will be presented.

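### No delta-adjusted or penalised analysis in the SAP keeps observed post-rescue values as its main analysis does, so the HbA1c tipping point is not a clean test of the missing-data assumption

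*SAP*

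**What the plan says.** **Primary analysis.** SAP 8.1.1 imputes missing HbA1c within arm and treatment-completion subgroup (the retrieved-dropout approach) and states that "values collected after the start of rescue medication will not be excluded". This imputation runs only if at least 3% of each arm, about 6 subjects, attended week 60 after stopping treatment. Otherwise the primary analysis is the MMRM on all available data. The same section plans that MMRM as a supportive ITT analysis in any case, and a per-protocol MMRM.

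**Tipping point.** SAP 8.1.2 item 1 reads: "Tipping point analysis will be conducted. Data after rescue medication will be considered as missing". Imputation is then by regression under MAR. The first imputed value is worsened by delta1 on bexagliflozin and improved by delta2 on glimepiride. Each delta runs from 0.1 to 0.5 in steps of 0.1, giving 25 pairs and no (0,0) cell. The titles of Table 14.2.1.4.2 and Figure 14.2.1.7 confirm the rescue exclusion. (The output index numbers this analysis 2; section 8.1.2 lists it first.)

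**Rescue analysis.** SAP 8.1.2 item 2 repeats the MMRM with post-rescue HbA1c set to missing, in order to examine the influence of those data.

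**Body weight.** SAP 8.2.1 keeps data after rescue in the main analysis. For the penalised imputation, SAP 8.2.4 says: "Values collected after the start of rescue medication will be considered missing".

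**The concern.** A tipping-point analysis should show how unfavourable the unobserved values must be before the conclusion changes, so it should vary only the assumption about those values. Compared with the retrieved-dropout primary analysis, item 1 changes three things at once:

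- observed post-rescue results are removed;
- imputation by completion subgroup becomes MAR regression;
- delta is applied to removed measurements as well as to values never obtained.

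The removed results are real data. Under Protocol 3.3.3.3 rescued subjects continue on investigational product, and HbA1c is scheduled through week 60.

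The stake is how the non-inferiority claim is read. If the grid tips, nobody can tell how much is due to missing data and how much to the treatment of rescued subjects. The SAP also leans on this analysis: section 13 drops LOCF on the ground that it adds nothing beyond the tipping point.

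**Working it through.** **Plan's own figures first.** Inputs from SAP 3.8: margin 0.35, SD 1.0, one-sided 0.025, 90% power. The true difference is not stated and is taken as 0.

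- n per arm = 2 × (1.960 + 1.282)² × 1.0² / 0.35² ≈ 171.6, rounded up to 172.
- 172 / (1 − 0.18) = 209.8, rounded up to 210.

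Both reproduce. The plan therefore treats 18% as having no usable week-60 value.

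**Assumptions not in the documents.** r is the share of subjects otherwise observed at week 60 who were rescued, taken as 5–20%. Delta is assumed to carry in full from the first imputed visit to week 60.

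**Share of shifted values that were observed.** With m = 0.18, the fraction treated as missing is f = m + r(1 − m), and the observed share is r(1 − m)/f.

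**Largest grid shift.** At (0.5, 0.5) with equal rescue, the shift in bexagliflozin minus glimepiride is f × (0.5 + 0.5) = f.

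**Tipping delta.** With 172 evaluable per arm the CI half-width is 1.96 × √(2/172) = 0.211. At an estimate of 0 this leaves 0.35 − 0.211 = 0.139. The common delta that tips the result is 0.139/(2f), holding the half-width fixed.

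| Rescue r | f | Observed share of shifted values | Shift at (0.5, 0.5) | Tipping delta per arm |
|---|---|---|---|---|
| Values kept (only unobserved shifted) | 0.18 | 0% | 0.18 | 0.39 |
| 5% | 0.18 + 0.041 = 0.221 | 19% | 0.22 | 0.31 |
| 10% | 0.18 + 0.082 = 0.262 | 31% | 0.26 | 0.26 |
| 20% | 0.18 + 0.164 = 0.344 | 48% | 0.34 | 0.20 |

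**Carry-over.** SAP 8.1.2 applies delta only to the first imputed value, so full carry is an upper case. At half carry, 0.18 becomes 0.09 and 0.22–0.34 becomes 0.11–0.17. The observed share does not change.

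**Unequal rescue.** Let g be the HbA1c benefit of rescue, and suppose imputation recovers the value without rescue. Deletion alone then moves the difference by (r_bex − r_glim) × (1 − m) × g. Negative values favour bexagliflozin.

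- 8% vs 15%, g = 0.8: −0.07 × 0.82 × 0.8 = −0.046. Reversed, +0.046.
- 5% vs 20%, g = 1.0: −0.15 × 0.82 × 1.0 = −0.123. The (0.5, 0.5) penalty is 0.5 × 0.221 + 0.5 × 0.344 = 0.283, so the net shift is 0.16. That is milder than the 0.18 obtained by shifting only unobserved values.
- 20% vs 10%, g = 1.0: +0.082. The penalty is 0.5 × 0.344 + 0.5 × 0.262 = 0.303, net 0.385, which is harsher.

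**The case against.** A reader might infer that nothing in the SAP tests the missing-data assumption behind the primary result. The documents do not support that, for three reasons.

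- The supportive ITT MMRM in 8.1.1 keeps post-rescue values and replaces the retrieved-dropout assumption with ordinary MAR. When the retrieved-dropout analysis is primary, this changes the missing-data assumption alone.
- Every cell of the grid still shifts the values that are truly missing. With equal rescue in the two arms it tips earlier than a grid limited to those values, so a result that survives it would survive the cleaner version.
- Section 8.1.2 declares that it addresses missing data and rescue together, and item 2 serves roughly as the absent zero-delta reference. Comparing the supportive MMRM with item 2 shows the effect of rescue handling; comparing item 2 with the grid shows the effect of delta.

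Two extensions also fail. The hypoglycemia analysis in 8.2.4 does discard post-rescue data ("Data collected after the start of rescue medication will be considered as missing"), but it is a negative binomial model with exposure ended at rescue; nothing is imputed or shifted. And the protocol's first sensitivity analysis, multiple imputation in which "HbA1c values collected after the start of rescue medication will not be excluded", carries no stated delta or penalty. If the 3% trigger fails, a MAR imputation would largely repeat the MMRM, so its omission loses no adverse-direction test.

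One may also prefer to remove rescue values in a non-inferiority setting, because rescue can pull the arms together. That is a reason to show a rescue-excluded grid as well, not to have it as the only one.

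What remains is narrower. The MAR check is not adverse in direction, and in the fallback case it is the primary analysis itself, leaving no ITT analysis that varies the assumption with post-rescue values kept. Item 2 cannot remove the fact that delta falls on both kinds of value.

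**Conclusion.** The concern holds as a mismatch between the stress tests and the analyses they are meant to stress, for HbA1c (8.1.2 item 1 against 8.1.1) and for body weight (8.2.4 against 8.2.1). The grid tests the missing-data assumption, but confounded with rescue handling.

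Under the stated assumptions 19–48% of the shifted values would be observed results, and the largest shift would be 0.22–0.34 rather than 0.18. For an estimate of 0 the tipping delta would fall from about 0.39 to between 0.31 and 0.20. With equal rescue this errs on the strict side; with unequal rescue it can be stricter or more lenient. Only the 18% and the margin come from the plan. The rescue rates, rescue benefit and carry-over are assumed, so the figures show sensitivity and do not predict the result. The primary estimate itself is unaffected.

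**What to change.** - **SAP 8.1.2 item 1:** retain observed post-rescue HbA1c as in 8.1.1, impute and shift only unobserved values, and add a (0,0) cell so the grid has its own reference.
- **Existing grid:** keep the rescue-excluded version as an additional display, and title Table 14.2.1.4.2 and Figure 14.2.1.7 so that each version is clearly labelled.
- **SAP 8.2.4:** add a version of the penalised body-weight imputation that retains observed post-rescue values.

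The cost is SAP wording, a data flag in the existing programs and one more set of sensitivity runs. No new data are needed. The change should be made before unblinding.
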